7.4.4 Vital Signs, Physical Examinations, and Other Assessments

Vital signs including body temperature, respiratory rate, and heart rate (after 5-minute rest) will be measured once at Screening and throughout the trial at the visits indicated in the Schedule of

Assessments. Arterial blood pressure (after 5-minute rest) will be measured twice using a validated device and recorded at the visits indicated in the Schedule of Assessments ([Appendix 1: Schedule of Assessments](#)).

A complete physical examination (including, e.g., general appearance, skin, head/neck, pulmonary, cardiovascular, gastrointestinal, external genitourinary, lymphatic, musculoskeletal system, extremities, eyes [inspection and vision control], nose, throat, and neurologic status) will be performed at screening and at subsequent visits as documented in the Schedule of Assessments ([Appendix 1: Schedule of Assessments](#)) and the abnormal results documented in the CRF. All clinically significant abnormalities occurring before signature of informed consent should be recorded in the Medical History section and/or Disease History; all abnormalities occurring or worsening after signature of informed consent should be recorded in the AEs section. Abnormal findings are to be reassessed at subsequent visits.

Body weight will be recorded at Baseline as indicated in the Schedule of Assessments ([Appendix 1: Schedule of Assessments](#)) and documented in the CRF. All newly diagnosed conditions, signs, and symptoms observed from screening, whether related to trial medication or not, are to be reported as AEs. The relapse will not be reported as an AE and will be captured in a dedicated eCRF page for efficacy analysis.

CCI

8 Statistics

CCI

CCI

8.2 Randomization

Not applicable.

8.3 Endpoints

8.3.1 Primary Endpoint(s)

- Differences in the counts of CUA MRI lesions during the first 6 months (i.e. during periods months 1-6, 2-6, 3-6) compared to baseline (i.e. the period screening to baseline).

8.3.2 Secondary Endpoints

- Characterization of immune cell subsets count at the end of 3, 6, 12, 15, 18 and 24 months compared to baseline

8.3.3 Tertiary Endpoints

Safety:

- Occurrences of TEAEs and SAEs including and up to 24 months

Clinical:

- Changes in SDMT outcome at the end of 6, 12, 18 and 24 months compared to baseline
- Disability evolution as measured by EDSS/KFS, 9HPT, T25FW at the end of 6, 12, 18 and 24 months compared to baseline
- ARR between baseline and 24 months
- Changes in CUA lesions during the following post-baseline periods compared to the baseline period (i.e. the period from screening to baseline):
 - Period of month 6 to month 12

- Period of month 1 to month 12
- Period of month 18 to month 24
- Period of month 1 to month 24

Further periods and comparisons may be defined in the SAP

- Number of CUA lesions during the baseline and post-baseline periods as defined above
- Changes in active T1 Gd+ lesion count at the end of 1, 2, 3, 6, 12, 15, 18 and 24 months compared to baseline
- Volume changes of T1 Gd+ lesions at the end of 1, 2, 3, 6, 12, 15, 18 and 24 months compared to baseline
- Number of T1 hypointense lesions at the end of 1, 2, 3, 6, 12, 15, 18 and 24 months compared to baseline
- Change in volume of T1 hypointense lesions at the end of 1, 2, 3, 6, 12, 15, 18 and 24 months compared to baseline
- Changes in new T2 lesion count during the post-baseline periods compared to the baseline period as defined above
- Responder rate during the different periods as defined above with responder being defined as subjects with a CUA lesion count reduction of at least 1
- Changes in T2 lesion volume at the end of 12 and 24 months compared to baseline
- Changes in MTR at the end of 1, 2, 3, 6, 12, 15, 18 and 24 months compared to baseline
- Changes in brain volume at the end of 1, 2, 3, 6, 12 and 24 months compared to baseline (and changes at 24 months compared to 6 months to exclude pseudo-atrophy)
- NEDA at 24 months
- NEPAD at 24 months

CCI

CCI

CCI

8.4 Analysis Sets

The following analysis sets are defined:

- Enrolled Set: all subjects who provided informed consent
- ITT (intent-to-treat) Set: all subjects classified as eligible
- FAS (Full Analysis Set): all subjects from the ITT who received at least one dose of the trial treatment
- Treatment Completer Set – Year 1: All subjects from the FAS who completed the full treatment course of the first year.
- Treatment Completer Set – Year 2: All subjects from the FAS who completed the full treatment course of the first and the second year.
- Safety set: all subjects who have received at least one dose of the trial treatment.

The primary analysis and all efficacy analyses will be performed on the FAS. As a robustness analysis the primary analysis will be repeated on the ITT (if different from the FAS) and the Treatment Completer Sets. All safety analyses will be performed on the Safety set.

Subjects who have withdrawn consent for the trial will be included in the analysis unless it was specified by them that their data not be used, after clarification of the level of withdrawal by the Investigator.

8.5 Description of Statistical Analyses

8.5.1 General Considerations

All analyses of all endpoints except the primary analysis, will be performed exploratively and, differences with a p-value of 0.05 or less will be considered nominally statistically significant.

Parameter estimates with associated 95% confidence intervals (CIs) will be reported in each analysis. No correction for multiple testing will be applied for any secondary or tertiary analysis.

Subjects' demographic factors and baseline clinical characteristics will be summarized with the following measures: mean with standard deviation, minimum and maximum for normally distributed continuous variables, median with interquartile range, minimum and maximum for other continuous variables and counts with percentages for categorical variables.

As the secondary and tertiary analysis set concerns repeated measurements of outcomes for each individual, it is likely that observations pertaining to each individual will be correlated. Furthermore, as this is a multi-center trial, it is likely that clustering of individuals within trial sites will produce an additional source of correlation. Mixed-effects regression, whereby a three-level hierarchical model is specified for observations within subjects within trial sites, will be used to account for within-subject and within-center correlation (Gibbons, 2010).

The parametric assumptions underlining the regression models specified will be examined. Should these assumptions be violated, alternative methods, such as non-parametric approaches, may be considered in addition.

Assessment Schedules

It is likely that the second year treatment may be delayed substantially due to grade 3 or 4 lymphopenia for a small number of subjects for whom the second dose is not required immediately. Due to the need for a finite follow-up period, a buffer of 3 months is given for subjects who do not receive the second treatment at the specified time. Subjects for whom treatment is delayed by over 3 months may not have all assessment data captured and as such, these observations will be treated as missing in efficacy analyses.

In each analysis, should assessment be delayed, subjects' assessment data will be treated as though it occurred at the time point specified and inferences will be conducted accordingly.

Missing Data

Should missing data be present in baseline covariates included in the analysis models, mean or median imputation and use of a missing indicator will be used for continuous and categorical covariates, respectively.

The trial dataset comprises of multiple outcome assessments made for each subject over a 24-month period. Therefore, due to the longitudinal nature of the data and the lengthy follow-up period, it is likely that missing outcome data will be present due to loss to follow-up.

In addition to the primary analysis model which is assuming missing at random (MAR), multiple imputation methods assuming different patterns of missingness will be applied to evaluate the robustness of results (see Section Robustness Analyses for more details).

8.5.2 Analysis of Primary Endpoints

The primary endpoint(s) for the trial are differences in counts of CUA MRI lesions during the first 6 months compared to baseline, i.e. the following differences will be evaluated:

- Period of month 3 to month 6 compared to the baseline period (i.e. the period of screening to baseline).
- Period of month 2 to month 6 compared to the baseline period,
- Period of month 1 to month 6 compared to the baseline period.

The differences in counts of CUA lesions will be evaluated using a mixed-effects linear model, accounting for within-center/region correlation through a hierarchical model.

The analysis will also adjust for baseline factors deemed to be prognostic for the primary endpoint, as judged by clinical experts:

- CUA lesion count during the baseline period,
- age,
- EDSS (≤ 3 / > 3).

The analysis will also adjust for the difference length and number of MRIs of the periods to be compared.

The difference in the counts of CUA lesions during the 3 periods compared to the baseline period will be tested in a sequential order. The 3 hypotheses are defined as follows:

$$H_{0i}: \Delta \text{CUA}(t_i) \geq 0 \quad \text{vs} \quad H_{1i}: \Delta \text{CUA}(t_i) < 0, \quad i=1,2,3$$

with

$$\Delta \text{CUA}(t_i) = \# \text{CUA}(p_i) - \# \text{CUA}(p_0), \quad i=1,2,3,$$

$$\# \text{CUA}(p_i): \text{count of CUA lesions during period } p_i, \quad i=0,1,2,3,$$

p_0 : baseline period (period screening to baseline),

p_i : period month i to month 6, $i=1,2,3$.

The sequential testing procedure will start with period p_3 , followed by period p_2 and p_1 , i.e., the hypotheses will be tested in the following order:

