4.1 Primary Objective

- To determine the onset of action of Mavenclad® in subjects with highly active relapsing multiple sclerosis (RMS).

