- In all other cases the missing onset day or missing onset month will be replaced by 1 (but not before start of study medication).

In all subject data listings, imputed values will be presented and flagged.

Missing statistics, e.g. when they cannot be calculated, should be presented as “nd”. For example, if n=1, the measure of variability (e.g. SD) cannot be computed and should be presented as “nd”.

Where tables are presented over time, the total number of subjects with missing and non-missing observations at each time-point should reflect the population still in the study at that time. This does not apply when imputations are made beyond study withdrawal.

Data Handling for MRI data

Data handling of Primary endpoint(s) and its components:

The MRI lesions will be evaluated by independent central review, which will provide the following measurements for the primary endpoints (see IRC for Counting Brain MRI Lesions [3]):

- Total number of T1 Gadolinium enhancing lesions (T1 Gd+) (or Not Evaluable [NE], if applicable) at the first and last MRI of the respective Period,
- Total number of new T2 lesions with T1 Gd+ (or NE, if applicable) of the respective Period (comparing the last with the first MRI of the respective Period),
- Total number of enlarging T2 lesions with T1 Gd+ (or NE, if applicable) of the respective Period (comparing the last with the first MRI of the respective Period),
- Total number of new T2 lesions without T1 Gd+ (or NE, if applicable) of the respective Period (comparing the last with the first MRI of the respective Period),
- Total number of enlarging T2 lesions without T1 Gd+ (or NE, if applicable) of the respective Period (comparing the last with the first MRI of the respective Period).

The statistical analysis will use the results from the Global assessment (i.e. Readtype=GLOBAL).

The assignment of MRIs to the respective Visits (e.g. assignment of ET MRIs or delayed MRIs due to steroid treatment) will be ensured by the central reading process. MRIs taken while on Steroid Treatment as identified as a major PD will be excluded from the analysis.

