All derived lesion counts (except for the Mean T1 Gd+ lesion count) as specified below will be classified as NE if one of the components required for the calculation has been classified as NE by the central reading. The Mean T1 Gd+ lesion count will be set to NE only, if all T1 Gd+ lesion counts that correspond to the respective Period are classified as NE. In all other cases the mean will be calculated based on the available counts during the respective Period.

T1 Gd+ lesion count

As with this procedure a Visit is assessed multiple times for the T1 Gd+ and thus T1 Gd+ will be reported multiple times per Visit, the value for a Visit of the earliest available Period will

be selected for the statistical analysis. As the Global Review will ensure that all duplicates have identical lesion count, this rule does not have an impact on the number of T1 Gd+ but defines further attributes (e.g. date of review).

The T1 Gd+ counts for a Period will be defined as the sum of the T1 Gd+ lesions from all scheduled MRI scans reported for a Visit that is included in a Period divided by the actual number of MRI scans with a reported lesion count (i.e. not NE) during a Period.

- T1 Gd+ lesion count (by Visit) = T1 Gd+ lesions count from the MRI at the respective Visit
- Mean T1 Gd+ lesion count (by Period) = T1 Gd+ lesion count during the Period / # of scans belonging to the respective Period with non-missing T1 Gd+ lesion count.

MRIs are assigned to a Period as follows:

- Baseline Period:
 - Screening Visit
 - Baseline Visit
- Period 1:
 - Month 1 Visit
 - Month 2 Visit
 - Month 3 Visit
 - Month 6 Visit
- Period 2:
 - Month 2 Visit
 - Month 3 Visit
 - Month 6 Visit
- Period 3:
 - Month 3 Visit
 - Month 6 Visit

Active T2 lesion count

As the new or enlarging T2 lesion count depends on the length of the Period, it will be presented as reported (non-standardized) and standardized to 1 months (30.4375 days):

- Period length (days) = MRI date at end of Period – MRI date at start of Period +1,
- Standardized total T2 lesion count (by Period per 1 months) = Total number of T2 lesions per Period * 30.4375 / Period length.

The following types of T2 lesions are defined per Period (standardized and non-standardized):

- Total new T2 lesion count =
Total number of new T2 lesions with T1 Gd+
+ Total number of new T2 lesions without T1 Gd+
- Total enlarging T2 lesion count =
Total number of enlarging T2 lesions with T1 Gd+
+ Total number of enlarging T2 lesions without T1 Gd+,

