- Total active T2 lesion count =
Total new T2 lesion count
+ Total enlarging T2 lesion count

The total active T2 Lesion count will also be reported for the Baseline, Month 2, Month 3, and Month 6 Visit and is defined as:

- Total active T2 Lesion count = Total number of new or enlarging T2 lesions since the scan of the previous Visit

and will be calculated as follows:

- Total active T2 Lesion count at the Baseline Visit
= Total active T2 Lesion count of the Baseline Period
- Total active T2 Lesion count at the Month 2 Visit
= Total active T2 Lesion count of Period 1 (M1-M6) – Period 2 (M2-M6)
- Total active T2 Lesion count at the Month 3 Visit
= Total active T2 Lesion count of Period 2 (M2-M6) – Period 3 (M3-M6)
- Total active T2 Lesion count at the Month 6 Visit
= Total active T2 Lesion count of Period 3

For the calculation of the CUA lesion count, only T2 lesions that did not emerge from a T1 Gd+ lesion will be taken into account.

- Total active T2 lesion count (without T1 Gd+) =
Total new T2 lesion count without T1 Gd+
+ Total enlarging T2 lesion count without T1 Gd+

and will be standardized to the length of the Period. Total active T2 lesion count (without T1 Gd+) will only be calculated if T1 Gd+ counts for beginning and end of the corresponding Period are non-missing.

CUA lesion count

The number of CUA lesions for a Period will be defined as the sum of the T1 Gd+ and new or enlarging T2 counts for the respective Period and will be standardized to one scan (for T1) or one month (for T2) to harmonize the units of the 2 assessments.

- #CUA(p_i) = Standardized CUA lesion count (by Period i per 1 month)
= Mean T1 Gd+ lesion count (by Period i per Visit)

+ Standardized total active T2 lesion count (without T1 Gd+)
(by Period i per 1 months)

The CUA lesion count will only be calculated if both components (T1 and T2) are non-missing.

Data handling of Tertiary endpoints:

The MRIs will be evaluated by independent central review (see IRC for Lesion Counting for the Tertiary Endpoint [6]). As the central reading process for Tertiary MRI Endpoints is different from the process for Primary MRI Endpoints, data are provided in a different format (see Data Transfer Specification [8]).

The assignment of MRIs to the respective Visits will be ensured by the central reading process and may differ from the initial MRI Visit assignments as reported in the eCRF. The statistical analysis is based on the MRI assignments as provided by central reading.

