 - and any Lymphocyte count < 800 cells/mm³ at or after Month 12 Visit and before start of Treatment Course 2.
- Before or at / after Start of COVID-19 pandemic

The cumulative dose is defined as the sum of the number of tablets taken 10 mg divided by the weight for treatment year:

Cumulative dose = number of tablets taken in Treatment Course 1 * 10mg / weight in kg at Baseline + number of tablets taken in Treatment Course 2 * 10mg / weight in kg at Month 12b Visit.

The cumulative dose will be calculated only if the weight and number of tablets are available. Otherwise it will be missing. If the Treatment Course 2 wasn't started (i.e. no tablet taken in Treatment Course 2), the cumulative dose will be calculated only for the Treatment Course 1.

A subject data listing of the treatment compliance will be provided for the SAF.

14 Efficacy Analyses

The following sections describe the planned analyses for each of efficacy endpoints.

For the detailed definition of covariates and stratification factors that are used in the statistical models see Section 9. Details about the derived MRI endpoints and general handling of MRI data is described in Section 9 (“Data Handling of MRI data”).

Descriptive summary statistics will be presented for the absolute values and the changes from Baseline as applicable by Visit [Protocol Scheduled Visits except for Baseline (defined in Section 9)], or Period, for all efficacy endpoints (and the components, where applicable) for the FAS and respective subgroups or subsets for which the variables are analyzed. Details about the presentation of continuous and categorical variables are given in Section 9.

Wherever possible, all estimated results from the statistical models will be calculated with the same observed margin which reflects the population of the whole corresponding analysis set, regardless of missing data.

14.1 Primary Endpoints: Differences in the counts of CUA MRI lesions during the first 6 months compared to Baseline

The primary endpoints for the trial are defined as the differences in counts of CUA MRI lesions during the first 6 months compared to Baseline, i.e., the following differences will be evaluated:

1. Period of Month 1 to Month 6 compared to the Baseline Period.
2. Period of Month 2 to Month 6 compared to the Baseline Period.
3. Period of Month 3 to Month 6 compared to the Baseline Period.

For the detailed definition of Periods, please see Section 9 “Data Handling of MRI data”.

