14.1.1 Primary Objective: Analysis of primary endpoints

The differences in counts of CUA lesions will be evaluated using a mixed-effects linear model, accounting for within-center/region correlation through a hierarchical model. The analysis will adjust for Baseline factors deemed to be prognostic for the primary endpoint, as judged by clinical experts:

- CUA lesion count during the Baseline Period,
- Age,
- EDSS at Baseline ($\leq 3 / > 3$).

The results of the mixed-effects linear model will be used to describe the effect size. A review of Baseline data has shown that the distribution of the primary endpoint data does not follow Normal distribution. Consequently, the hypotheses will be tested by a Wilcoxon signed-rank test which employs ranks of absolute differences from Baseline for each testing Period (i.e., p_1 , p_2 , and p_3) using average ranks for tied values.

The analysis will also adjust for the difference in length and number of MRIs of the Periods to be compared (see Section 9 “Data Handling of MRI data” for details of lesion count standardization).

The difference in the counts of CUA lesions during the three Periods compared to the Baseline Period will be tested in a sequential order. The three hypotheses are defined as follows:

$$H_{0i}: \Delta \text{CUA}(p_i) \geq 0 \quad \text{vs.} \quad \Delta \text{CUA}(p_i) < 0, \quad i = 1, 2, 3$$
$$\Leftrightarrow H_{0i}: \#\text{CUA}(p_i) \geq \#\text{CUA}(p_0) \text{ vs. } \#\text{CUA}(p_i) < \#\text{CUA}(p_0), \quad i = 1, 2, 3$$

with

$$\Delta \text{CUA}(p_i) = \#\text{CUA}(p_i) - \#\text{CUA}(p_0), \quad i = 1, 2, 3,$$

$$\#\text{CUA}(p_i): \text{standardized CUA lesion count during Period } p_i, \quad i = 0, 1, 2, 3,$$

p_0 : Baseline Period (Period from Screening to Baseline),

p_i : Period Month i to Month 6, $i = 1, 2, 3$.

The sequential testing procedure will start with Period p_3 , followed by Period p_2 and p_1 , i.e., the hypotheses will be tested in the following order:

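### The confirmatory tests are nested averages that all end at Month 6, so rejecting the Month 2–6 or Month 1–6 hypothesis cannot date the effect to Month 2 or Month 1

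*Protocol*

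**What the plan says.** Protocol 4.1 gives one primary objective: "To determine the onset of action of" Mavenclad in highly active relapsing MS. Protocol 8.5.2 defines three differences in CUA lesion count against the screening-to-baseline period, for Months 3–6, 2–6 and 1–6. The widest reads "Period of month 1 to month 6 compared to the baseline period", and SAP 14.1 repeats it as "Period of Month 1 to Month 6 compared to the Baseline Period". On testing, SAP 14.1.1 says: "The difference in the counts of CUA lesions during the three Periods compared to the Baseline Period will be tested in a sequential order". The order is H03, H02, H01. Each is a one-sided signed-rank test at 2.5%, and testing stops at the first non-rejection.

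SAP 9 defines the count. The T1 part is a mean over scans: "T1 Gd+ lesion count during the Period / # of scans belonging to the respective Period" with a non-missing count. The T2 part comes from "comparing the last with the first MRI of the respective Period", scaled to one month. Only active T2 lesions without T1 Gd+ enter, and that component "will only be calculated if T1 Gd+ counts for beginning and end of the corresponding Period are non-missing".

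By-visit results are also planned. SAP 6.1 and 14.3.3 put T1 Gd+ by visit in the 6-month analysis. For active T2, SAP 9 says: "The total active T2 Lesion count will also be reported for the Baseline, Month 2, Month 3, and Month 6 Visit". SAP 14.3.1 and 14.3.7 add annualised CUA and active T2 by visit from Month 1 onward. Protocol 8.5.1 makes everything outside the primary analysis exploratory and without multiplicity correction.

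**The concern.** The objective asks when the drug starts to work. The hypotheses are indexed by starting month and tested from the latest start to the earliest, so the sequence looks like a walk back in time. But each step keeps all the scans behind the previous step and adds one earlier scan. The Month 3 and Month 6 scans sit in every window, and every T2 comparison ends at Month 6. A late effect can therefore lower all three averages. If a rejected H01 were reported as a confirmed effect from Month 1, the trial would answer its main question with a result that does not address it.

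**Working it through.** **1. The plan's own claim.** In a fixed sequence the first true null hypothesis is tested at 0.025, so the familywise error is 0.025. A simulation with no effect gave 0.025 (1,500 runs). The statement that no adjustment is needed is correct for the hypotheses as written.

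**2. How much of a late effect enters each window.** The inputs are the scan assignments and formulas in SAP 9. T1 share = scans after onset / scans in the window. T2 share = months after onset within the window / window length.

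| Window (scans) | Onset after Month 3 scan: T1, T2 | Onset after Month 2 scan: T1, T2 |
|---|---|---|
| p3 (M3, M6) | 1/2, 3/3 = 1.00 | 2/2, 1.00 |
| p2 (M2, M3, M6) | 1/3, 3/4 = 0.75 | 2/3, 4/4 = 1.00 |
| p1 (M1, M2, M3, M6) | 1/4, 3/5 = 0.60 | 2/4, 4/5 = 0.80 |

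With an 85% effect starting after the Month 3 scan, the T1 part of p1 falls by 0.25 × 85 = 21% and the T2 part by 0.60 × 85 = 51%, although nothing has changed at Months 1, 2 or 3. This step needs no assumed data.

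**3. How often the tests then reject.** From the documents: N = 265, one-sided 2.5%, the testing order, the visit schedule and the CUA formula. Assumed: 0.25, 0.5 or 1.0 new lesions per month; gamma variation between subjects (shape 0.5 or 1); 30.4 days of enhancement; a screening-to-baseline gap of 28–97 days; no effect until day 90, then a fixed reduction in new lesions. There were 2,000 runs per setting (Monte Carlo error at most 1.1 points). Two readings of 'without T1 Gd+' were run: not enhancing at the last scan, or at any scan in the window.

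| Late-only reduction | H02, last-scan | H01, last-scan | H01, any-scan |
|---|---|---|---|
| 85% (H03 100%, last-scan) | 79–100% | 34–76% | 99.7–100% |
| 70% | 49–95% | 14–26% | 64–100% (50–70% pooled) |
| 60% | 24–74% | 5–7% | as above |
| 50% | 9–31% | 0.7–1.6% | as above |

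Sensitivity at 85%, last-scan: 3-week enhancement gives H02 97–100% and H01 67–99%; 45-day enhancement gives 57–98% and 16–32%; N = 240 gives 75–100% and 31–72%.

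A second model drew T1 and T2 counts separately by visit, with late reductions of 50–90%. It gave H02 84–100% and H01 61–100% for onset after the Month 3 scan, and H01 98–100% for onset after the Month 2 scan.

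**4. Separating nesting from standardisation.** In the model of step 3, CUA is not flat even with no effect. Means in p1 / p2 / p3 are 1.24 / 1.20 / 1.14 of baseline (last-scan) or 0.96 / 1.03 / 1.14 (any-scan), because scan numbers and window lengths differ. The same windows and order were therefore applied to mean T1 Gd+ and to total active T2 per month. There the no-effect mean is 1.00–1.01 of baseline and the p1 test alone rejects in 0.2–2.6%. A late 85% effect then rejects p2 in 82–100% and p1 in 51–96% (T1), and p2 in 100% and p1 in 99–100% (T2). Nesting alone carries the late effect into the earlier windows.

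**5. What does separate early from late.** Under the last-scan reading, mean p1 CUA is 0.86 of baseline for a late-only 85% effect and 0.87 for a 30% effect from day 0. The p3 means differ (0.46–0.47 against 0.80). T1 Gd+ at the Month 3, 2 or 1 scan against the Baseline scan rejects in 1.8–3.4% of late-only runs, close to nominal.

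**The case against.** The strongest reply is that the plan never says what is being criticised. A reader might infer from the objective and the order of tests that rejecting H01 is meant to prove an effect by Month 1. The documents do not support that inference: each hypothesis is written as a window difference, and the estimates to be reported are differences for the specified periods. A reader might also infer a type I error fault, or that no timing evidence is planned. Neither is so, as step 1 and the by-visit analyses show. This part of the reply stands. Protocol 8.1 and Appendix 11 are redacted and could contain an interpretation rule.

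The rates also depend on assumptions. A late-only 85% effect is a test case, not a forecast. Under the last-scan reading a late 50–60% effect rejects H01 in under 7% of runs. The T2 counting rule lies in an independent review charter that is not available. The last-versus-first comparison and the need for T1 counts at both ends lean towards the last-scan reading. The statement in SAP 9 that counted T2 lesions must not have emerged from a Gd+ lesion leans towards lesion history. That leaves the size for CUA open. It does not touch the weights in step 2.

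What remains is that no visible passage connects the test results to a time of onset, or says which results will carry that statement.

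**Conclusion.** The point holds as a limit on interpretation. H02 and H01 are valid tests of average activity over Months 2–6 and 1–6. They cannot date an effect to Month 2 or Month 1, because an effect absent through the Month 3 scan still enters p2 with weights 1/3 and 0.75 and p1 with weights 1/4 and 0.60.

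How often this would mislead depends on the size of the late effect, the lesion rate, the duration of enhancement and the unseen counting rule. For a strong late effect, H02 would usually be rejected, and H01 anywhere from about a third of the time to always. For a weaker late effect under the last-scan reading, H01 would seldom be rejected. The data needed to speak about timing are already planned, so what needs settling is which results support the onset statement.

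**What to change.** Keep the three primary tests, their order and the 2.5% level.

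1. State in SAP 14.1 and in the report that rejecting H02 or H01 shows lower average activity over that window only.
2. Base any statement on onset time on non-overlapping results: T1 Gd+ at the Month 6, 3, 2 and 1 scans, each against the Baseline scan. Give estimates and 95% confidence intervals for all four, beside active T2 by visit. In the 6-month analysis active T2 has no Month 1 value.
3. Do not make these depend on H01. Under the last-scan reading, a late 50–70% effect rejects H01 in only 0.7–26% of runs, so the scan contrasts would stay closed in about 74–99%, even at Month 6.
4. If a fixed order (Month 6, 3, 2, 1) is wanted, run it on its own and label it post hoc, because SAP 7 shows that the primary analysis has been performed. In the second model this order, with onset only after the Month 3 scan, wrongly declared Month 3 in 1.8–3.3% of runs and Month 2 in at most 1.0%. T1 Gd+ suits such a test because it holds its level with no effect (2.0–3.2%). Active T2 per month at Months 2 and 3 does not (2.8–7.9%), because interval lengths differ.
5. Report the earliest scan with a shown reduction as 'effect shown by' that scan, not as the time of onset, since low power can make it late.

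The cost is a paragraph and one table; no new scans or reads are needed. Power per scan is lower. When the order was tried after the primary sequence, a true 30% effect from day 0 at 0.25 lesions per month reached Month 1 in only 9–15% of runs. Without that gate the share cannot be lower, but it was not computed. Timing would rest on T1 Gd+ rather than CUA, the results carry no confirmatory weight, and regression to the mean in a single-arm comparison remains.
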